5 OBJECTIVES

5.1 Broad Objective

To assess the combined impact of RTS,S (malaria) vaccination and PBO nets on *Plasmodium* infection and transmission, and how they interact when they are introduced together.

5.2 Specific Objectives

The specific objectives for the study are as follows:

1. To estimate the impacts of PBO nets and RTS,S vaccine on the prevalence and transmission of *Plasmodium* infection. (Phase 1).
2. To assess the feasibility of evaluating the impact of RTS,S vaccine and PBO nets on the prevalence and transmission of *Plasmodium* infection in a larger scale study. (Phase 2).

6 METHODS

6.1 Study Design

This will be a prospective cohort study. This is a preliminary study to determine if we can detect an impact of RTS,S vaccine combined with PBO nets on parasitological, entomological and/or serological evidence of infection and transmission. If this preliminary study yields significant results, we will have the opportunity to apply for funding from our sponsor (US National Institutes of Health) for a much larger study that will assess the impact of each of these interventions individually and how they interact with each other. If we are approved to conduct this multi-arm study, we will submit a new protocol to COMREC and the MSU IRB for review and approval.

Using malaria and vaccine registers, we will establish community-based cohorts of children age-eligible to receive RTS,S vaccination from the two extreme groups: i.e. Nyambi health centre in Machinga and Kalembo health centre in Balaka. The Machinga district, is undergoing implementation of both RTS,S vaccination and PBO nets (RTS,S and PBO interventions). Balaka households do not receive RTS,S vaccination and only receive conventional nets arms (Table 1). We will enroll children of the age that would be eligible for vaccination and all of the children over nineteen months and under ten years of age in their house. We will conduct interviews and collect specimens at enrolment and at 2, 4 and 6 months, as described below. During these visits, data on individual, household, social, and behavioral determinants, immunization status, ITN use will be collected.

Table 1: Overview of study design and methods

Specific Objective 1: To estimate the impact of PBO nets and RTS,S vaccine on Plasmodium infection prevalence and transmission in Malawi.		
Methods	Data sources	Key variables/ outcome

Phase 1: Recruited from Nyambi Machinga health centre – in catchment areas that receive RTS,S vaccination and PBO nets.
 
Recruited from Kalembo health centre in Balaka – in catchment areas that receive conventional nets and no malaria vaccination.
	
Interviews of parent/guardians participantsBlood samplesCaptured mosquitosHuman reporting about NetsFinger prick blood specimens	
Plasmodium falciparum infectionGametocyte presenceAnopheles spp. abundanceAnopheles gravidityAnopheles sporozoite rateNet usageImmunization statusSerological markers

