6.2 Study location

The study will be carried out in Machinga and Balaka Districts, in Southern Malawi. *Machinga District* (14.55 S, 35.40 E), located ~120 km northeast of Blantyre, is a poor rural district. Malaria transmission is intense and year-round, peaking during the rainy season (November through May). Between July 2013 and June 2014, an estimated 162,500 (1-year risk of 28%) malaria cases were reported and accounted for 24% of the total Outpatient Department (OPD) attendance (the total population of Machinga District is ~572,000 people). In 2015, malaria annual incidence was 367 cases/1,000 individuals. The use of ITNs is widespread in the district; findings from the 2015-2016 MDHS reported that 66.3% of the individuals and 80.5% of under-five children slept under an ITN in the previous night.

Balaka District (15.01° S, 35.01° E), forms a boundary with Machinga and is also a poor, rural district. Malaria is generally high in the district with intense, year-round transmission that also peaks during the rainy season. Between July 2013 and June 2014, malaria cases were accounted for 29% of the total OPD attendance (the total population of Balaka District is ~372,000 people). In 2015, malaria annual incidence was 310 cases/1,000 population. Findings from 2015-2016 MDHS indicated that 67.5% of the population and 87.3% of under-five children slept under an ITN in the previous night.

The timing for this proposal is optimal as we will be able to take advantage of the Malawi government-funded nationwide ITN distribution campaign (2018) and the RTS,S evaluation project (2019). In November 2018, Malawi undertook a country-wide bed net campaign, distributing nets to each household with a target of one net for every two people. In Machinga district, PBO nets were distributed, while neighboring Balaka District conventional pyrethroid-treated bed nets were given. About eight months later, both districts are part of the vaccination of infants and young children with the RTS,S vaccine, where children in selected clusters will receive RTS,S whilst children in some clusters of the same district would act as controls. The Malawi Ministry of Health has asked our ICEMR team, through the College of Medicine Malaria Alert Centre, to support the evaluation of RTS,S vaccination, thus providing a perfect opportunity to assess the combined effects of these interventions.

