6.3.2 Sample size

Our sample size estimates are based on previous high and low transmission season surveys conducted during the first ICEMR (2010–2017) in areas similar to the clusters that will be selected for this study. Based on these data, we anticipate that 13%-18% of households will contain a child 7-18 months old. The risk of infection in this age group is estimated to be 21% (30% high and 20% low transmission seasons). In children \leq 10 years of age the risk of infection is estimated to be 31% (46% in the high and 32% in the low transmission seasons). The within-cluster correlation is estimated at 0.004 (0.05 in the high and 0.00 in the low transmission seasons) and 0.14 (0.22 in the high and 0.06 in the low transmission seasons) for children aged 7-18 months and \leq 10 years of age, respectively. Based on these data, by studying the 25 clusters with 20 households with a child 7-18 months per intervention arm, we will analyze 500 children aged 7-18 months and a similar or larger number of older children. For power calculations, we assumed that these proportions represented the risk of incident cases of infection.

This proposed sample size will allow us to estimate moderate effectiveness of the combined interventions (versus no intervention) with 80% power in 2-sided tests, accounting for within-cluster correlation, and with α -level of 0.05. For instance, based on the cross-sectional estimations of individual risk of malaria infection obtained at enrollment of each cohort, we will be able to

detect the effectiveness of 34% (36% and 33% when stratifying by season) in children 7-18 month-old (Hayes, 2009). In a repeated measure analysis, with within-subject correlation of 1.5 to 2 times larger than within-cluster correlation, we will be able to detect effectiveness of 34-37% in children 7-18 month old (Liu, 2002).

For entomological assessments, 100 households from each of the two arms will be visited for entomological analysis including *Anopheles* abundance, female mosquito parity, and source of blood meal and sporozoite prevalence. Based on our previous experience, we have found an average of one *Anopheles* mosquito per household sampled (although with very heterogeneous distribution), and 75-95% human-biting prevalence.

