6.4 Participant recruitment and study procedures

Participant recruitment. Prior to recruiting participants, households in which children have received RTS,S and PBO nets will be identified. (PBO+, RTS,S+). Additionally, through vaccination records, we will identify households in Balaka where children who received the full scheme of Pentavalent (Diphtheria-pertussis-tetanus; Hepatitis B; Haemophilus influenzae type b) vaccine and have received a standard bed net live. In Nyambi catchment area, by the end of September, an estimated 260 children are expected to be vaccinated with RTSS vaccine. Thus, to achieve an adequate sample size for the significant inferential statistics, children will be enrolled from the Health Centre and tracked back in the community. Children will be identified and RTS,S information will be extracted from the registers by the research team. With the help from the health surveillances Assistants (HSAs) and community health volunteers (CHVs), RTS,S age-eligible children (7-18 months old) will be tracked using information obtained from the registers back to their villages and households where children will be enrolled and followed up for the designated study period. In the Kalembo catchment area, the same process that will be employed in Nyambi will be adopted. However, to make the cohort more comparable, using under two EPI vaccine register, children who completed three doses of Pentavalent (Diphtheria-pertussis-tetanus; Hepatitis B; Haemophilus influenzae type b) vaccine and are in RTS,S vaccine age-eligible will be considered in Kalembo.

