7.3.2 Known Potential Benefits

This study will enroll children aged 7 months to 10 years within two government HC catchment areas. In Malawi, this age group is at greatest risk of malaria infection and its complications. The participants will benefit from being intensively followed-up during the six months specifically at (0, 2, 4, and 6 months) study period, and by having mRDT results provided and treatment provided, if indicated at 1 and 6 months. The research team will give the participants health advice and refer them for treatment at the local health center. The study team will support the local health center with laboratory services and drugs so that all participants will be guaranteed access to laboratory diagnostics of malaria and or antimalarial treatment where necessary. The individuals who participate in this study will have access to prompt diagnosis and treatment of malaria when appropriate. We are

going to perform mRTDs to participants at recruitment and 6 months. Similarly, we will also test participants for anemia at recruitment and at all the follow up months. By participating in this study, the children will have access to high-quality and personalized medical attention. In the case of life-threatening emergencies, the study team will use their vehicle to transfer the study participants to the nearest government or private hospital. The minimal risks of this study, associated with finger pricks and the breaches of confidentiality are outweighed by these benefits. In addition, the study will provide support to the health centre in the study with resources mainly in malaria diagnosis and treatment which will benefit the community at large, not just research participants. In addition, the results of this study will help to maximize the implementation and impact of malaria prevention and control measures throughout Malawi. Each enrolled household will be given K2000 for each study visit as compensation for their transport cost during enrolment and monthly visits.

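### Arm and catchment are the same variable, so the stated 80% power and 5% alpha for an intervention effect hold only if Nyambi and Kalembo have equal underlying infection risk after adjustment

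*Combined protocol and SAP*

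**What the plan says.** Section 6.1 describes a non-randomised prospective cohort recruited "from the two extreme groups: i.e. Nyambi health centre in Machinga and Kalembo health centre in Balaka". Table 1 gives Nyambi the vaccine and PBO nets, and Kalembo conventional nets and no malaria vaccine. Section 7.3.2 confirms that there are only two catchments: "This study will enroll children aged 7 months to 10 years within two government HC catchment areas".

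Section 6.3.2 obtains 500 children aged 7-18 months per arm "by studying the 25 clusters with 20 households with a child 7-18 months per intervention arm". It claims to estimate moderate effectiveness of the combined interventions against none "with 80% power in 2-sided tests, accounting for within-cluster correlation", at an alpha of 0.05. From the enrolment cross-sections it expects to "detect the effectiveness of 34% (36% and 33% when stratifying by season) in children 7-18 month-old".

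On comparability, section 6.4 restricts Kalembo: "to make the cohort more comparable, using under two EPI vaccine register, children who completed three doses of Pentavalent" are considered there. Section 6.5 compares baseline data by compliance with each intervention, partly to look for confounding and selection bias, and will explore causal models because of vaccination adherence. Section 4 expects serology to allow control for exposure. Section 6.5 names no covariate set for the effectiveness models.

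Section 6.1 makes a significant Phase 1 result the opening to apply for funding of a larger multi-arm study. Table 2 schedules a Go/No-Go assessment after Phase 1.

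**The concern.** All 25 clusters in an arm lie in the same catchment. Correlation among clusters inside Nyambi, or inside Kalembo, says nothing about how the two places differ. With one catchment per arm there are no degrees of freedom to estimate that difference, and more children or clusters in the same two catchments would not help. Any difference in transmission, housing or care that remains after adjustment is added to the intervention effect, and neither the p-value nor the stated power reveals it.

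Enrolment prevalence is not a pre-intervention check. Nets were distributed in November 2018 (section 6.2), recruitment is set for December 2019 (Table 2), and the Nyambi children are identified from vaccination records (section 6.4).

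At stake is what Phase 1 can conclude: followed as written, the plan would credit a catchment difference to the vaccine and the nets.

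**Working it through.** **Inputs (section 6.3.2, ages 7-18 months).** 500 per arm in 25 clusters of 20. Control risk 0.21 pooled, 0.30 high season, 0.20 low season. Within-cluster correlation (ICC) 0.004, 0.05 and 0.00. Two-sided alpha 0.05.

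**Formulas.** Design effect D = 1 + 19 × ICC. Kalembo risk is p0. Nyambi risk is p1 = p0 × (1 − VE) × R, where VE is true effectiveness and R is the Nyambi/Kalembo infection risk ratio without the interventions, remaining after adjustment. SE = √{[p0(1 − p0) + p1(1 − p1)] × D / 500}. The chance of declaring benefit is Φ[(p0 − p1)/SE − 1.96]; of declaring harm, Φ[(p1 − p0)/SE − 1.96]. Apparent effectiveness is 1 − (1 − VE) × R.

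**Reproducing the plan at R = 1.** D is 1.076 pooled, 1.95 high season and 1.00 low season. The effectiveness giving 80% power is 33.1%, 35.3% and 32.9%, against the stated 34%, 36% and 33%. For example, pooled at 34%: p1 = 0.1386, SE = 0.0248, z = 0.0714/0.0248 = 2.88, power 82%. The ICCs alone account for the stated figures.

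**Letting R vary (pooled inputs).** The documents give no catchment-level risk, so R is an assumption shown over a range. The end points 1.184 and 0.845 are 367/310 and its inverse, from the 2015 district incidences in section 6.2.

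| R | False benefit (VE 0) | False harm (VE 0) | Power at VE 34% | 34% appears as | Power at VE 60% |
|---|---|---|---|---|---|
| 0.845 | 24.2% | 0.1% | 97.1% | 44.3% | >99.9% |
| 0.909 | 10.9% | 0.4% | 93.1% | 40.0% | >99.9% |
| 0.918 | 9.6% | 0.45% | 92.4% | 39.4% | >99.9% |
| 1.00 | 2.5% | 2.5% | 82.2% | 34.0% | >99.9% |
| 1.05 | 0.9% | 5.8% | 73.2% | 30.7% | >99.9% |
| 1.084 | 0.45% | 9.5% | 66.2% | 28.5% | 99.9% |
| 1.10 | 0.3% | 11.8% | 62.7% | 27.4% | 99.9% |
| 1.184 | <0.1% | 28.8% | 43.6% | 21.9% | 99.7% |

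Example, R = 0.845 with no true effect: p1 = 0.1774, SE = 0.0259, z = 0.0326/0.0259 = 1.26, and Φ(1.26 − 1.96) = 0.24.

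At the plan's seasonal targets, R = 1.184 lowers power from 82% to 47% (36%, high season) and from 80% to 40% (33%, low season).

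**Which way R might lie.** The district indicators conflict. Machinga: "In 2015, malaria annual incidence was 367 cases/1,000 individuals"; Balaka had 310. Yet malaria's share of outpatient attendance was 24% in Machinga and 29% in Balaka. Machinga's own figure is unstable: "an estimated 162,500 (1-year risk of 28%) malaria cases were reported and accounted for 24% of the total Outpatient Department (OPD) attendance" for 2013-14 gives 162,500/572,000 = 28.4%, so 2015 is 36.7/28.4 = 1.29 times as high. The direction of R is unknown.

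**How large the true effect might be.** Section 3.2 cites 33% second-year efficacy for PBO nets. Section 3.3 cites 50.4% vaccine efficacy against clinical malaria and 70-90% protection against microscopy-defined infection. If the two act independently (an assumption, and the endpoints differ), 33% with 50.4% gives 1 − 0.67 × 0.496 = 66.8%, and 33% with 70% gives 1 − 0.67 × 0.30 = 79.9%. At 66%, power exceeds 99.9% even at R = 1.184.

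**The case against.** The strongest reply is that stated power in any non-randomised comparison assumes no residual confounding. Section 6.1 openly calls the study preliminary and the groups extreme, and a new protocol would precede any multi-arm trial. This stands as an argument against redesign. It does not excuse section 6.3.2 from stating the condition when it claims power for an intervention effect.

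A reader might infer that a catchment difference in either direction inflates the chance of wrongly proceeding. It does not. At R = 1.084 two-sided error is about 10%, but false benefit is 0.45%, and false harm would not plausibly lead to a larger study. Nor are the Go/No-Go criteria given in the text, so how far a p-value drives that decision is unknown.

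A reader might also infer that the study is underpowered. The 34% is a minimum detectable effect, not an expected one, and at about 60% or more the power loss is negligible.

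Two further points stand in part. The ICCs come from earlier surveys not shown here, so they may contain some between-area variation; reproducing the figures shows only that no additional term was used. And R near 1 does modest damage: at R = 1.05, two-sided error is about 7% and power at 34% is 73%.

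The existing safeguards help but do not supply R = 1. The pentavalent rule aligns vaccine uptake, not transmission. The compliance comparison is close to a catchment contrast, but it describes differences without removing them. The causal models address adherence.

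**Conclusion.** The point holds as a missing condition, and should be fixed. In the powered contrast of both interventions against neither, arm is fully aliased with catchment, and only R = 1 preserves both the stated power and the stated alpha.

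The main consequence is bias and false benefit: from 2.5% at R = 1 to about 10% at R = 0.92 and 24% at R = 0.845. The estimate is biased in either direction; a true 34% reads as 44% at R = 0.845 and as 22% at R = 1.184. Power loss is secondary and confined to moderate effects. These sizes rest on the plan's pooled inputs and an assumed R; the district ratio is a proxy, not an estimate for these catchments or this age group. The 34-37% repeated-measures figure carries the same condition but was not recomputed.

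Three stronger readings are not supported: that the section 6.3.2 arithmetic is wrong (it reproduces), that Nyambi is known to have the higher risk (the indicators disagree), and that Phase 1 must be redesigned.

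**What to change.** 1. **Section 6.3.2.** State that each arm's 25 clusters lie in one catchment, and that the power and alpha are conditional on equal underlying risk in Nyambi and Kalembo after adjustment. Add a short table over R, for example 0.85 to 1.18, showing false benefit, false harm, power and apparent effect, labelled illustrative.
2. **Section 6.5.** Show baseline characteristics by catchment as well as by compliance. Make the main effectiveness estimate one adjusted for age, SES and house construction, all already collected. Change the intention in section 4 so that antibodies measured after the interventions are not adjusted for in that main model: they may lie on the effect pathway, and section 6.5 analyses them as an outcome. A serology-adjusted analysis can remain as secondary. State that unmeasured catchment differences remain.
3. **Section 6.1.** Word the Phase 1 conclusion as a difference between two catchments, and read statistical significance together with the sensitivity range in the Go/No-Go assessment of Table 2.

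The cost is protocol wording, one table and a little more analysis, with no extra participants, visits or samples. The downside is that the stated power looks less favourable, and adjustment removes only measured differences.

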6.3 Study Population

Children whose age is between 7 and 18 months, which indicates they could receive at least 3 RTS,S doses, will be eligible to participate. Following informed consent from parents/guardians, up to two children who are 18 months but \leq 10 years of age, from the same household as the vaccine-eligible child, will also be enrolled. Only households whose families intend to stay in the area for at least six months and whose eligible children will also be expected to use an assigned health center for child vaccinations will be eligible to participate.

Inclusion/Exclusion Criteria

To be eligible for the cohort, participants must meet all the following inclusion criteria:

- Children aged 7 to 18 months of age (age-eligible for at least 3 doses of RTS,S doses)
OR being one of not more than two children living in the household of an enrolled age-eligible child and being >18 mos and ≤ 10 years of age.
- Not on cotrimoxazole prophylaxis for HIV infection
- Weight >5 kg
- Permanent residence of Health Centre (HC) catchment area
- Residence within 10 km from the HC
- Written informed consent from parent/guardian for the child to participate in the study

Non-residents of the catchment area and visitors to the study area will be excluded because the study requires follow-up for at least 6 months and access to interventions such as conventional, PBO nets and malaria vaccination.

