6.3.1 Study period

We will conduct two consecutive cohort studies with 500 children in the desired age group in each arm, and we will also study up to two children >18 mos and \leq 10 years of age (anticipated one or two per household) in each household to obtain preliminary data about the impact on transmission in the household (Table 3). Children will be identified and enrolled after obtaining parental consent. They will undergo interviews and one finger-prick blood sample collection every two months for six months (2, 4, and 6 months) after enrollment. Household entomological sampling will occur during the rainy season.

Table 2: Timing of Phase 1 study visits and specimen collection

Timeline	Activity
May-November 2019	Finalizing research plan and approval by IRBs (CoM and MSU)
November 2019	Community consultation with community leaders, Staff recruitment and training, Developing practical arrangements and SOPs and developing the data management system
December 2019	Cohort recruitment
January- 2019-May2020	Cohort follow up (round 1)
May 2020-October 2020	Cohort recruitment and follow up (round 2)
November 2020-March 2021	Data analysis and assessment of Go/No-Go criteria

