In both catchment areas, up to two children in the household aged >18 months and \leq 10 years old residing with the vaccine age-eligible children will also be offered the opportunity to enroll. All invited children will be screened by a study nurse for eligibility using a screening form. During the screening process, the details of the study procedures that will take place in the cohort will be described in detail. For children who meet the eligibility criteria, parents/guardians will then be asked whether they are willing to have their child participate in the study and those that agree will be asked to sign the consent form. A copy of the signed consent form will be given to the head of the parent/guardian. All enrolled will be given a study identification number. Only children from the families intending to stay in the area whose parents provide written informed parental consent will be considered for enrollment. In addition, consent will be sought from the parent/guardian for entomological activities in the household.

Table 3: Overview of study procedures

Visit Type	Home Visit/enrollment	Two-monthly visits: Central location near home
Study procedure		
Potentially eligible participants identified through satellite imagery and predetermined clusters. Households are visited and those with eligible children identified	X	
Obtain informed consent to participate in the study	X	
Child demographic and HH socioeconomic information	X	
Through a finger prick, collect blood sample and DBS for quantitative PCR, serum separation, antibody quantification, preservation of RNA, and storage – done on every two months follow up for entire 6 months.	X	X
Structured questionnaire interview	X	X
ITN use and vaccination status	X	X
Participants reminded of their visit date	X	X
Household mosquito collection for testing		One time
Hemoglobin measurement	X	X
Malaria rapid diagnostic test	X	Final visit only

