To examine antibodies of exposure, two approaches will evaluate the association between levels of exposure antibodies and intervention groups: 1) antibody levels will be summarized using partial least square regression (PLS); 2) levels of individual antibodies will be used. Summary scores and antibody levels will be compared over time between the two groups through joint outcome (shared parameter) models (Verbeke, 2010). Moreover, joint outcome models will be fit for positivity of responses and a zero-inflated model will be fit for the breadth of responses (number of antibodies that are positive in a subject).

For analysis of effectiveness in all household members (in Phase 1, children aged >18 months and \leq 10 years old), indirect effectiveness at the individual level at four-time points will be estimated. Also, in nested random effect models for individual analysis, we will account for correlation across visits, within the household. The household-level analysis will be conducted by summarizing outcomes in the household, and also in nested random effect models, using the same link functions described above.

For entomological outcomes, analysis of effectiveness will be performed comparing intervention groups through zero inflated negative binomial models with random effects, including as offsets hours of capture effort or number of captured mosquitoes, as appropriate. Outcome variables will include abundance of *Anopheles*, sporozoite rates, blood-meal originated from humans, and female parity in households.

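### The protocol gives two conflicting enrolment rules for older household children, does not say which two enter under the cap, and leaves the household summary undefined

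*Combined protocol and SAP*

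**What the plan says.** All of this is current text of the combined protocol and SAP.

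- **6.1 Study Design** enrols "all of the children over nineteen months and under ten years of age in their house": no cap, lower limit above 19 months, upper limit below 10 years.
- **6.3 Study Population**, first paragraph, speaks of up to two children "from the same household as the vaccine-eligible child, will also be enrolled". It gives the lower limit simply as 18 months; a symbol may have been lost in the text available to us.
- **6.3, Inclusion/Exclusion Criteria**, admits an older child by "being one of not more than two children living in the household of an enrolled age-eligible child", aged over 18 months and up to 10 years.
- **6.3.1 Study period** repeats the cap and the over-18-months range, with "anticipated one or two per household".
- **6.4 Participant recruitment and study procedures** offers enrolment to "up to two children in the household aged >18 months" and up to 10 years. It gives no rule for choosing them.
- **6.3.2 Sample size** expects "a similar or larger number of older children" than the 500 index children per arm, without fixing it.
- **6.5 Analysis Plan** uses these children to estimate indirect effectiveness, and adds: "The household-level analysis will be conducted by summarizing outcomes in the household, and also in nested random effect models". The link functions are those already described (logistic for infection). The summary itself is not defined, nor is the handling of the number enrolled.

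**The concern.** Three things are left open.

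1. **Who is eligible.** Field teams in Nyambi and Kalembo could each follow a different section and both be within protocol.
2. **Who is chosen under the cap.** Where three or more children qualify, the parent or the field worker decides. Enrolment brings a rapid test, and treatment if it is positive (6.4, 7.3.2), which gives a reason to put forward an unwell child. The comparison is of one health-centre catchment with another, without randomisation, so nothing balances family size or field practice between arms.
3. **What is summarised by household.** Some summaries change in expected value with the number of children tested; others do not.

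At stake are the indirect-effectiveness estimate and the household-level comparison, which are this phase's evidence on transmission within the household. Nested random effects allow for correlation between children of one household. They do not allow for how those children came to be in the sample.

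**Working it through.** **The plan's own power figure.** Section 6.3.2 states a detectable effectiveness of 34% at ages 7-18 months. Inputs: risk 21%, within-cluster correlation 0.004, 25 clusters of 20 per arm, 80% power, two-sided 0.05. Effective size per arm = 500 / (1 + 19 × 0.004) = 500 / 1.076 ≈ 465. The detectable effectiveness is then 33.2% (33.6% by the cluster-trial formula), and power at 34% is 0.82. By season it is 35.5% (stated 36%) and 33.0% (stated 33%). The figure reproduces and does not involve the older children.

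**Does the cap matter for power in older children?** Hardly. Risk 31% and correlation 0.14 (6.3.2), with 25 clusters per arm and 20, 40 or 60 older children per cluster:

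| Older children per household | Per arm | Effective size | Detectable effectiveness |
|---|---|---|---|
| 1 | 500 | 137 | 46% |
| 2 | 1,000 | 155 | 44% |
| 3 | 1,500 | 162 | 43% |

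The issue is therefore selection and definition, not numbers.

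**The rules side by side.**

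| Child | 6.1 | 6.3 criteria, 6.3.1, 6.4 |
|---|---|---|
| Between 18 and 19 months | out | in |
| Third eligible older child | in | out |
| Exactly 10 years | out | in |

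**Selection under the cap (illustration).** Assume each eligible child is infected independently with probability 0.31, and two are taken one after the other with weight *w* for an infected child and 1 for an uninfected child. The weight is an assumption; the documents give none.

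Three eligible, *w* = 1.5:
- One infected, probability 3 × 0.31 × 0.69² = 0.4428: expected infected among the two = 1 − (2/3.5)(1/2.5) = 0.7714.
- Two infected, probability 3 × 0.31² × 0.69 = 0.1989: expected = 2 − [1 − (3/4)(1.5/2.5)] = 1.45.
- Three infected, probability 0.31³ = 0.0298: expected = 2.
- Prevalence = (0.4428 × 0.7714 + 0.1989 × 1.45 + 0.0298 × 2) / 2 = 0.345.

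Four eligible, *w* = 1.5: one to four infected have probabilities 0.4074, 0.2745, 0.0822 and 0.0092, with expected infected among the two of 0.619, 1.157, 1.614 and 2. Prevalence = (0.2522 + 0.3177 + 0.1327 + 0.0185) / 2 = 0.360.

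The same enumeration with other weights:

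| *w* | Two of three | Two of four |
|---|---|---|
| 1 (random) | 31.0% | 31.0% |
| 1.25 | 33.0% | 33.8% |
| 1.5 | 34.5% | 36.0% |
| 2 | 36.7% | 39.5% |

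With an assumed within-household correlation of 0.2, the *w* = 1.5 row becomes 33.8% and 35.0%. With one or two eligible children there is no choice to make, and prevalence stays at 31%. If a share *s* of enrolled older children come from households with three or four eligible, overall prevalence rises by *s* × 3.5 to *s* × 5.0 percentage points at *w* = 1.5. The documents do not give *s*.

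**Household summary.** With risk *p* = 0.31 and *k* children tested:
- Any positive, independent children: 1 − 0.69^*k*, so 31% for *k* = 1 and 1 − 0.4761 = 52% for *k* = 2.
- Any positive, *k* = 2, correlation 0.2 (assumed): 1 − (0.4761 + 0.2 × 0.31 × 0.69) = 1 − 0.5189 = 48%.
- Proportion positive: mean 31% for any *k*. Only its standard deviation changes, √[*p*(1 − *p*)(1 + (*k* − 1)ρ)/*k*]: 0.46 for *k* = 1 and 0.35 for *k* = 2 at ρ = 0.14 (assumed for households; the documents give only within-cluster values).

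**The case against.** The strongest reply is that the operative rule is clear. The cap stands in four places, including the formal criterion and the recruitment procedure, and 6.1 is one overview sentence. The older children supply preliminary data, no detectable effect is stated for them, and individual-level models are also planned. Section 6.4 records socio-economic status and which household members up to 10 years sleep under each net, so some information on household composition will exist.

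Much of this stands. The contradiction alone would be a wording repair. It does not answer the missing selection rule: the cap, however often repeated, is what creates the choice, and individual-level models do not undo it.

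Three stronger readings are tempting, and the documents do not support them.

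- **That the plan analyses a household infected/not-infected outcome.** It never says so. A logit link fits positives out of children tested equally well.
- **That the household comparison is biased by some 9-11%.** That needs an any-positive summary and an arm difference in the number enrolled. For example, if 60% of households in one area and 40% in the other enrolled two children, the ratio would be 1.09 to 1.11 with no true difference. Nothing in the documents suggests such a split. Nor can the any-positive figure for three children (67%) arise under the cap.
- **That outcome-related selection biases the arm comparison.** A preference that is equal in both areas raises both prevalences and largely cancels in the ratio. Because children with a positive rapid test at enrolment are treated, selection on current infection should also weigh most on the enrolment round and less at months 2, 4 and 6.

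The 31% risk is itself soft: it refers to all children up to 10 years, and it lies below both of its own seasonal values (46% and 32%).

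**Conclusion.** The point holds in a limited form. It is certain that the enrolment rules and age limits conflict, that no rule says which two children enter, and that the household summary is undefined. It is plausible but unquantified that selection will be related to infection. At an assumed 1.5-fold preference, prevalence among the chosen two is about 34% to 36% instead of 31%, in households with three or more eligible children only. Bias between arms needs the further condition that the preference, or the share of such households, differs between Nyambi and Kalembo. The plan neither prevents that nor would allow it to be detected, because the children left out are not listed. Dependence on the number enrolled arises with an any-positive summary (31% with one child, 48-52% with two) and not in the mean of a proportion. The detectable effects stated for ages 7-18 months are untouched. This should be changed before recruitment; it does not call the main comparison into question.

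**What to change.** 1. State one enrolment rule and one age range for older household children, and use the same wording in 6.1, 6.3 (paragraph and criterion), 6.3.1 and 6.4.
2. If the cap is kept, have the tablet form list every eligible older child in the household before consent is sought for any of them, and draw up to two at random. Record the number eligible, and any drawn child who is refused or absent.
3. In 6.5, define the household outcome as positives out of children tested, analysed as binomial, and say that the number eligible enters as a sampling weight or a covariate.

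The cost is protocol wording, a short listing screen and a random draw in the tablet form. No extra children, visits or samples are needed. It has to be in place before enrolment starts, because children who were never listed cannot be recovered at analysis.
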